5.3.2 Exclusion Criteria

Subjects who fulfill any of the following should not be enrolled into this trial:

1. Use of oral corticosteroids > 10 mg daily prednisone equivalent, use of injectable corticosteroids, or change in dose of corticosteroids within 2 weeks prior to Screening or during Screening
2. Initiation or change in dose for nonsteroidal anti-inflammatory drugs (NSAIDs) within 2 weeks prior to Screening
3. Treatment with tofacitinib, other BTK inhibitors, or a biologic DMARD (eg, anti-TNF- α , tocilizumab [anti-interleukin-6 receptor], abatacept [CTLA4-Fc]), or other immunosuppressive drugs (sulfasalazine would be acceptable at a stable dose) other than MTX within 3 months prior to Screening or during Screening
4. Treatment with anti-CD20 therapy (eg, rituximab) within 12 months prior to Screening or during Screening
5. Immunologic disorder other than RA, with the exception of secondary Sjogren's syndrome associated with RA, and well-controlled diabetes or thyroid disorder, or any other condition requiring oral, intravenous, intramuscular, or intra-articular corticosteroid therapy
6. Vaccination with live or live-attenuated virus vaccine within 1 month prior to Screening
7. Severe drug allergy or history of anaphylaxis, or allergy to the IMP or any of its excipients
8. Active, clinically significant viral, bacterial, or fungal infection, or any major episode of infection requiring hospitalization or treatment with parenteral anti-infectives within 4 weeks of Screening or during Screening, or completion of oral anti-infectives within 2 weeks before or during Screening, or a history of recurrent infections (ie, 3 or more of the same type of infection in a 12-month rolling period). Vaginal candidiasis, onychomycosis, and genital or oral herpes simplex virus considered by the Investigator to be sufficiently controlled would not be exclusionary
9. History of or positive testing for human immunodeficiency virus (HIV), hepatitis C antibody and/or polymerase chain reaction, hepatitis B surface antigen (HBsAg) (+) and/or hepatitis B core total, and/or IgM antibody (+) at Screening
10. History of or current diagnosis of active tuberculosis (TB); undergoing treatment for latent TB infection (LTBI); untreated LTBI (as determined by documented results within 3 months of the Screening Visit of a positive TB skin test with purified protein derivative with induration ≥ 5 mm, a positive QuantiFERON®-TB test or positive or borderline T-SPOT [Elispot] test); or positive QuantiFERON-TB test at Screening. Subjects with documented completed appropriate LTBI treatment would not be excluded and are not required to be tested.
 - Subjects with current household contacts with active TB will also be excluded.

- Indeterminate QuantiFERON-TB or T-SPOT tests may be repeated once, and will be considered positive if retest results are positive or indeterminate.

11. History of splenectomy at any time, or any major surgery within 2 months prior to Screening
12. History of myocardial infarction or cerebrovascular event within 6 months prior to Screening, or current active angina pectoris, symptomatic heart failure, uncontrolled seizures, untreated hypertension, GI bleeding, or any other significant active medical condition in the Investigator's opinion
13. On anticoagulation or antiplatelet therapy other than daily aspirin for cardioprotection
14. On fish oil (unless discontinued prior to first dose)
15. History of cancer, except adequately treated basal cell or squamous cell carcinoma of the skin (no more than 3 lesions requiring treatment in lifetime) or carcinoma in situ/cervical intraepithelial neoplasia of the uterine cervix, unless considered cured > 5 years
16. Breastfeeding/lactating or pregnant women
17. Clinically significant abnormality on ECG, or an active infective process or any other clinically significant abnormality on Screening chest X-ray (CXR) taken within 4 weeks of the first dose, per Investigator opinion. If a CXR has been taken within the previous 3 months and results are available and normal, the CXR does not need to be carried out
18. Estimated glomerular filtration rate by the 4-variable Modification of Diet in Renal Disease equation (19) of < 45 mL/min/1.73 m²
19. TSH < 0.01 or ≥ 7.1 mIU/L at Screening
20. Alanine aminotransferase (ALT), aspartate aminotransferase (AST), amylase, or lipase > 2X above upper limit of normal (ULN) of laboratory reference range, total bilirubin > 1.5X ULN, any other clinically significant laboratory abnormality
21. B cell (CD19) count < 50% of the lower limit of normal at Screening
22. Significant cytopenia, including absolute neutrophil count < 1,500/mm³, platelet count < 100,000/mm³, or absolute lymphocyte count < 1,000/mm³
23. Has taken an investigational drug within 1 month or 5 half-lives of the investigational drug, whichever is longer, prior to Screening
24. Subjects currently receiving (or unable to stop using prior to receiving the first dose of IMP) medications or herbal supplements known to be potent inhibitors of cytochrome (CYP)3A (must stop at least 1 week prior), potent inducers of CYP3A (must stop at least 3 weeks prior), or drugs mainly metabolized by CYP3A with a narrow therapeutic index (must stop at least 1 day prior).

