5.1 Overall Trial Design and Plan

This is a Phase IIa randomized, double-blind, placebo-controlled trial in approximately 64 subjects 18 to 75 years of age with RA on stable MTX background therapy.

Total duration of subject participation is approximately between 5 months (20 weeks) to 11 months (46 weeks), which includes:

- Screening: 28 days (4 weeks)
- Treatment: 84 days (12 weeks)
- Optional 6-month open-label extension period (26 weeks)
- Safety Follow-Up: 28 days (4 weeks)

After completing the 12-week treatment period, subjects will be offered the opportunity to participate in an optional 6-month open-label extension period where all subjects will receive M2951. For subjects who choose to participate in the optional extension period, the duration of participation will last a total of approximately 11 months.

Subjects who continue to receive M2951 during the extension period will also be required to undergo the Safety Follow-up Visit scheduled for approximately 28 days after the last treatment visit.

Screening will occur over Day -28 to -1 (Visit 1), during which time all Screening assessments must be completed and reviewed.

On Day 1 (Visit 2), after confirmation of eligibility, assessment of RA disease activity and vital signs, and obtaining of required blood and urine samples, subjects will be randomly assigned 1:1 to receive M2951 or placebo in combinations with MTX. **CCI**

Blood and urine samples will be obtained for safety (hematology, biochemistry, coagulation, and urinalysis), markers of disease activity (hsCRP, ESR, anti-CCP, and RF), PK (M2951 concentration), and PD (immunoglobulin levels, **CCI**, and B cell numbers) following the schedule detailed in the Schedule of Assessments ([Table 1](#)).

CCI

Subjects will self-administer the IMP at a set time each day (\pm 2 hours). Subjects must take their daily dose more than 1 hour prior to a meal or snack or more than 2 hours after a meal or snack. Clear fluids are allowed at any time. On trial visit days, the IMP will be administered during the trial visit after the trial visit procedures (other than PK/PD sampling) are completed.

[figure not shown]
Subjects will have trial visits weekly for the first 3 weeks of treatment; bi-weekly up until 8 weeks of treatment; a final On-Treatment Visit on Day 85 (12 weeks), and then return for 1 Follow-Up Visit approximately 28 days (4 weeks) after the last dose of IMP.

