10. History of vaccinations as follows: 1) against Streptococcus pneumoniae with PPSV23 or PCV13 with repeat administration as necessary to be up to date as per local guidelines; and 2) against influenza virus (as seasonally required); or vaccination against these pathogens during Screening. Subjects receiving 1 or more of these vaccinations during Screening must have at least 2 weeks between the vaccination(s) and the date of randomization

11. Signed and dated informed consent indicating that the subject has been informed of all the pertinent aspects of the trial prior to enrollment and will comply with the requirements of the protocol.

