5.4 Criteria for Randomization and Initiation of Trial Treatment

Randomization should occur on Day 1 (Visit 2) after all Screening procedures have been completed; subject eligibility must be reviewed again and confirmed at the site on Day 1 prior to randomization. If a subject does not meet eligibility criteria, the subject can be retested and rescreened once at the Investigator's discretion as described in Section 7.1.1.

Eligible subjects will be randomized to treatment with M2951 (50 mg bid) or placebo through a central randomization process by an Interactive Web Response System (IWRS). This will be a double-blind trial. **CCI**

5.5

Criteria for Subject Withdrawal

Subjects will be informed they have the right to withdraw from the trial at any time, without prejudice to their medical care, and they are not obliged to state a reason for withdrawing. Any withdrawal must be fully documented in the electronic case report form (eCRF) and source documents, and should be followed up by the Investigator.

The Investigator may withdraw a subject at any time if this is considered to be in the subject's best interest.

5.5.1

Withdrawal from Trial Therapy

Subjects who withdraw from therapy must immediately return for an End of Treatment Visit followed by the Safety Follow-Up/End of Trial Visit 4 weeks later. A subject must be withdrawn from M2951 or placebo if any of the following occur:

- Adverse events, if discontinuation of IMP is desired or considered necessary by the Investigator and/or subject
- Use of prohibited medications, as defined in Section 6.5.2. However, any medications that are considered necessary for the subject's well-being may be given at the discretion of the Investigator.
- Pregnancy
- Protocol noncompliance judged as significant by the Investigator and/or the Sponsor
- Subject withdrew consent
- Subject lost to follow-up
- Lack of efficacy
- Death
- Participation in another investigational clinical trial.

Withdrawal due to special precautions are described in Section 6.5.4.

5.5.2

Withdrawal from the Trial

Subjects may withdraw from the trial at any time without giving a reason. Withdrawal of consent will be considered withdrawal from the trial. Subjects who withdraw from the trial while still on the IMP should return immediately for an End of Treatment Visit upon discontinuation of the IMP and a Safety Follow-Up Visit 4 weeks after the last administered dose of IMP. Subjects who

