6.5 Concomitant Medications and Therapies

All concomitant medications taken by the subject during the trial from the date of signature of informed consent (including those participating in and during the extension period) are to be recorded in the appropriate section of the eCRF, noting the name, dose, duration, and indication of each drug. Nondrug interventions and any changes to a concomitant medication or other intervention should also be recorded in the eCRF.

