6.5.2 Prohibited Medicines

The following medications and therapies are not permitted during the trial and would require discontinuation of the trial treatment:

- Initiation of an immunosuppressant or immunomodulator, or increase in immunosuppressant beyond the maximum allowable dose
- Oral corticosteroid dose > 10 mg/day or use of intramuscular or intravenous steroids
- Intra-articular steroids
- Biologic therapies
- Intravenous Ig therapy and/or plasmapheresis
- Live and live-attenuated vaccines
- Herbal supplements including, but not limited to, St. John's wort, grapefruit, Seville oranges, cranberries, or juices of these fruits
- Moderate or strong inhibitors or inducers of CYP3A or drugs mainly metabolized by CYP3A with a narrow therapeutic index (see Table 2). The additive effects of weak inhibitors taken in combination must also be taken into account.

New therapies for RA should not be initiated during the trial. Initiation of any new immunosuppressant or immunomodulatory therapy would be considered a treatment failure and should result in withdrawal of the subject from the IMP (see Section 5.5.1).

Table 2

Examples of Inhibitors or Inducers of CYP3A Enzymes or Substrates with Narrow Therapeutic Range

Inhibitors		
Strong	Moderate	Weak
Boceprevir, clarithromycin, conivaptan, grapefruit juice, ^a indinavir, itraconazole, ketoconazole, lopinavir/ritonavir, mibefradil, nefazodone, neflifinavir, posaconazole, ritonavir, saquinavir, telaprevir, telithromycin, voriconazole	Amprenavir, aprepitant, atazanavir, ciprofloxacin, darunavir/ritonavir, diltiazem, erythromycin, fluconazole, fosamprenavir, grapefruit juice, ^a matinib, verapamil	Alprazolam, amiodarone, amlodipine, atorvastatin, bicalutamide, cilostazol, cimetidine, cyclosporine, fluoxetine, fluvoxamine, ginkgo, goldenseal, soniazid, nilotinib, oral contraceptives, ranitidine, ranolazine, tipranavir/ritonavir, zileuton
Inducers		
Strong	Moderate	Weak
Avasimibe, carbamazepine, phenytoin, rifampin, St. John's wort	Bosentan, efavirenz, etravirine, modafinil, naftilin	Amprenavir, aprepitant, armodafinil, echinacea, pioglitazone, prednisone, rufinamide
Substrates With a Narrow Therapeutic Range		
Alfentanil, astemizole, ^b cisapride, ^b cyclosporine, dihydroergotamine, ergotamine, fentanyl, pimozide, quinidine, sirolimus, tacrolimus, terfenadine ^b		

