7.4.1.3 Definition of the Adverse Event Reporting Period

The AE reporting period for safety surveillance begins when the subject is initially included in the trial (date of first signature of informed consent/date of first signature of first informed consent) and continues until the Safety Follow-Up/End of Trial Visit.

Any SAE occurring within 30 days after the last dose of IMP must be reported, even if the subject has discontinued from the trial. Any SAE assessed as related to the IMP must be reported whenever it occurs, irrespective of the time elapsed since the last administration of the IMP.

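### The live-vaccine exclusion stops at Screening, so the eligibility list admits a subject given a live virus vaccine in the 28 days before first dose

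*Protocol*

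**What the plan says.** Exclusion 6 in Protocol Section 5.3.2 is "Vaccination with live or live-attenuated virus vaccine within 1 month prior to Screening". The same text stands in the protocol synopsis and in SAP Section 6.

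On timing, Section 5.1 states: "Screening will occur over Day -28 to -1 (Visit 1), during which time all Screening assessments must be completed and reviewed". Section 5.4 adds a second look, in that "subject eligibility must be reviewed again and confirmed at the site on Day 1 prior to randomization", but that review uses the same criteria.

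Inclusion 10 in Section 5.3.1 expects some subjects to be vaccinated against pneumococcus or influenza while in Screening, and sets a gap: "Subjects receiving 1 or more of these vaccinations during Screening must have at least 2 weeks between the vaccination(s) and the date of randomization". It names the pneumococcal products but does not say what type of influenza vaccine may be used.

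Section 6.5.2 opens with "The following medications and therapies are not permitted during the trial and would require discontinuation of the trial treatment" and lists "Live and live-attenuated vaccines". It gives no washout before first dose. Section 5.5.1 makes use of a prohibited medicine a reason to stop the investigational product, while leaving the Investigator free to give medicines the subject needs.

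In SAP Appendix 3, PDEV17 records live virus vaccination as a deviation tied to exclusion 6 and adds no time window.

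**The concern.** The purpose of exclusion 6 is to keep a recent live vaccine away from the start of an immunomodulator. As worded, it bars the older exposure and passes the newer one. A site working from the eligibility list has no criterion that stops randomization of someone given a live virus vaccine during Screening. Two parts of the protocol can also be read differently on whether that vaccine was prohibited at all.

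Protocol Section 3.1 names infection among the important potential risks of M2951, and every subject is also on methotrexate. What is at stake is the safety of the individual subject. Sample size, power, the significance level and the primary comparison are not affected.

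There is a smaller mismatch of scope: exclusion 6 is limited to virus vaccines, while Section 6.5.2 covers all live vaccines.

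**Working it through.** The plan gives no figure to reproduce. The check is date arithmetic on the eligibility windows, followed by a comparison of the texts that bear on Section 6.5.2.

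**Inputs**
- First dose is on Day 1 and there is no Day 0 (SAP Section 11, treatment day), so Day -d is d days before first dose.
- The Screening visit and consent fall on Day -s, with s from 1 to 28 (Protocol Section 5.1).
- One month is taken as 30 days. This is the SAP Section 11 convention for time windows and is an assumption here, because exclusion 6 does not define a month.
- Inclusion 10 requires at least 14 days from a Screening influenza or pneumococcal vaccination to randomization, which is on Day 1.

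**Formulas, in days from vaccination to first dose, eligibility criteria alone**
- Barred by exclusion 6: s + 1 to s + 30.
- Not barred, because given during Screening: 1 to s.
- Influenza vaccine during Screening under inclusion 10: 14 to s.
- Shortest interval admitted if exclusion 6 also covered Screening: s + 31.

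| | Screening visit Day -28 (s = 28) | Screening visit Day -14 (s = 14) |
|---|---|---|
| Barred now | 29 to 58 | 15 to 44 |
| Not barred now | 1 to 28 | 1 to 14 |
| Influenza vaccine in Screening allowed at | 14 to 28 | exactly 14 |
| Shortest admitted interval after the fix | 28 + 31 = 59 | 14 + 31 = 45 |

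**Could the phrase about the time before Screening be meant to include Screening?** No. Exclusions 1, 3, 4 and 8 each name the time before Screening and then add Screening itself, so the protocol treats them as two periods.

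**Does Section 6.5.2 close the gap?** That depends on when the trial starts for a subject, and the protocol points both ways.

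- *For a start at consent.* Section 6.5 speaks of medications "taken by the subject during the trial from the date of signature of informed consent". Section 7.4.1.3 starts adverse event reporting "when the subject is initially included in the trial (date of first signature of informed consent". Section 5.1 counts Screening within the total duration of participation.
- *For a start after Screening.* Section 7.1.1 has subjects join the trial only once Screening is complete and eligibility is met. Section 6.5.1 names the Screening Period separately from the subject's participation. Exclusion 24 lets narrow-index CYP3A substrates continue until a day before first dose, although Section 6.5.2 prohibits the same class; a start at consent would set those two rules against each other.

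On either reading, Sections 6.5.2 and 5.5.1 call for stopping treatment. Neither bars enrolment or sets an interval before first dose.

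**Live vaccines other than virus vaccines.** If Section 6.5.2 starts at consent, only vaccination before consent is uncovered, and the shortest such interval is s + 1: 29 days for s = 28 and 15 days for s = 14. If it starts after Screening, these vaccines are uncovered at any time before first dose.

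**The case against.** The strongest reply is that Section 6.5 already handles the case. Its opening text is the nearest statement of scope for Section 6.5.2 and dates the trial from consent. The contrary texts can be explained: Section 7.1.1 describes moving on to enrolment, Section 6.5.1 may only be emphatic, and exclusion 24 is a specific washout rule that overrides a general one. On that view a live vaccine in Screening is already prohibited, and randomizing the subject would make no sense when the same protocol requires treatment to stop. Concomitant medications are recorded at Screening and Day 1, and the Investigator may withdraw a subject in the subject's interest. PDEV36 and PDEV41 in the SAP would catch the vaccine as well as PDEV17.

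The reading from consent is reasonable and may be what was intended. It does not settle the matter. The protocol did not rely on Section 6.5.2 to cover Screening for biologics, immunosuppressants or steroids above the limit: exclusions 1, 3 and 4 cover Screening for these explicitly. The consequence in Section 6.5.2 still presupposes that treatment has begun, and the safeguards rest on the Investigator's judgement. The SAP entries flag deviations after the event and do not prevent dosing.

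It is also true that exclusions 2, 11, 12 and 23 end at Screening, so criterion 6 is not an isolated drafting slip. None of those four has a counterpart in the Section 6.5.2 list. Among the Section 6.5.2 items that do have a matching exclusion, live vaccines are the one whose window stops at Screening.

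The objection is right on frequency. The documents give no vaccination counts and mention no live influenza product, and the intervals show what could happen, not how often it would. If Section 6.5.2 does start at consent, the change to inclusion 10 is a clarification only.

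**Conclusion.** The concern holds. On the eligibility criteria alone, a live virus vaccine given 1 to 28 days before first dose does not exclude a subject with a full-length Screening, while one given 29 to 58 days before does. Section 6.5.2 may prohibit the more recent vaccine, depending on when the trial is taken to start, but no text sets an explicit bar to enrolment or a washout before first dose.

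The day counts rest on a 30-day month and on consent falling on the day of the Screening visit. The ambiguity of Section 6.5.2 and the absence of an enrolment bar do not depend on either assumption. This is a safety-wording gap that should arise rarely among 64 subjects. It is worth correcting because the correction is so cheap.

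**What to change.** - In exclusion 6 (Protocol Section 5.3.2) and the matching bullets in the protocol synopsis and SAP Section 6, add *or during Screening* after the existing window and delete *virus*, so that the criterion has the same scope as Section 6.5.2.
- In inclusion 10, state that any influenza vaccine given during Screening must be a non-live product.

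For a live virus vaccine, the shortest interval to first dose that exclusion 6 admits then rises from 1 day to 59 days with a Screening visit on Day -28, or 45 days with one on Day -14. The cost is a few words in a protocol amendment and, at most, an occasional screen failure or delayed randomization. No analysis changes.

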PDEV35	Subjects receiving medications, herbal supplements, or food known to be moderate or strong inhibitors of CYP3A or drugs mainly metabolized by CYP3A (see Section 6.5.2 of CTP)	Yes	Yes	Eligibility and Entry Criteria	Exclusion criteria #24	If identified by medical review or corresponding exclusion criterion is ticked Yes.
PDEV36	Concurrent treatment with a non-permitted drug or procedure (refer to section 6.5.2 of CTP).	Yes	case by case basis			If identified by medical review.
PDEV37	Incorrect treatment group IP dispensed to subject	Yes	case by case basis	IP Compliance		If randomized treatment is different from actual treatment
PDEV38	Non-compliant with IP usage	Yes	case by case basis	IP Compliance		Check if <80% of >120%
PDEV39	IP not taken in compliance with protocol eg, at the appropriate times, during/timed with meals/snacks	case by case basis	case by case basis	IP Compliance		From monitoring log/Medical Review
PDEV40	Subject did not sign ICF and was enrolled	Yes	Yes	Informed Consent Criteria		ICF date is greater than randomization date

Protocol Deviation number	Protocol Deviation	Important	Clinically Important	Type criteria	Inclusion/Exclusion criteria number	Check
PDEV41	Subject used prohibited medication(s)	case by case basis	case by case basis	Other Criteria		Medical review
PDEV42	Lab safety and/or PK samples not drawn according to protocol requirements	case by case basis	case by case basis	Laboratory Assessment Criteria		Monitoring deviation log, Medical review

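### Exclusion 24 bars only potent CYP3A inhibitors and inducers, but moderate ones require stopping IMP on trial, and SAP PDEV35 codes moderate inhibitors as breaches of exclusion 24

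*Protocol*

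**What the plan says.** **Entry.** Protocol 5.3.2, exclusion 24, covers "medications or herbal supplements known to be potent inhibitors of cytochrome (CYP)3A", and also "potent inducers of CYP3A (must stop at least 3 weeks prior), or drugs mainly metabolized by CYP3A with a narrow therapeutic index". It gives a minimum stopping interval for each class it names: 1 week, 3 weeks and 1 day respectively.

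**On trial.** Protocol 6.5.2 lists "Moderate or strong inhibitors or inducers of CYP3A or drugs mainly metabolized by CYP3A with a narrow therapeutic index" under the lead-in "The following medications and therapies are not permitted during the trial and would require discontinuation of the trial treatment". Protocol 5.5.1 includes "Use of prohibited medications, as defined in Section 6.5.2" among the events for which a subject must be withdrawn from M2951 or placebo. It then adds that the investigator may give medication considered necessary for the subject's well-being.

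**Deviation coding.** SAP Appendix 3, PDEV35, is an eligibility and entry deviation assigned to exclusion criterion 24, with both Important and Clinically Important set to Yes. It refers to medications, herbal supplements or "food known to be moderate or strong inhibitors of CYP3A or drugs mainly metabolized by CYP3A", and points to Protocol 6.5.2. PDEV36 and PDEV41 deal separately with non-permitted or prohibited medication.

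**The concern.** Three rules that should describe one restriction have three different scopes. A site that follows exclusion 24 exactly can randomise a subject whose current medication triggers a mandatory IMP stop as soon as it is taken on trial.

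Two things are at stake. First, such a subject is lost to treatment for a reason known before randomisation. SAP 16.1 counts anyone who discontinues before Week 12 as an ACR20 non-responder, and Protocol 5.5.2 does not allow replacement. Second, the deviation listing can report as an entry violation something the entry criterion does not forbid.

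**Working it through.** The point rests on the text, so the first step is to set the three rules side by side.

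| CYP3A class | Exclusion 24 (entry) | 6.5.2 with 5.5.1 (on trial) | PDEV35 text (tied to exclusion 24) |
|---|---|---|---|
| Potent/strong inhibitor | Barred | Prohibited, IMP stopped | Named |
| Moderate inhibitor | Not named | Prohibited, IMP stopped | Named |
| Potent/strong inducer | Barred | Prohibited, IMP stopped | Not named |
| Moderate inducer | Not named | Prohibited, IMP stopped | Not named |
| Narrow-index substrate | Barred | Prohibited, IMP stopped | Named, but without the narrow-index limit |

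**Is moderate distinct from potent?** The protocol does not define potent. The notes to Table 2 separate strong inhibitors (substrate AUC raised at least 5-fold) from moderate ones (at least 2-fold but below 5-fold). Nothing extends potent to the moderate class.

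**Following one subject.** Take a subject on diltiazem, which Table 2 lists as a moderate inhibitor.
1. Exclusion 24 is not met, and the Day 1 eligibility check in Protocol 5.4 finds no breach of it. The subject can be randomised.
2. If the drug continues after randomisation, 6.5.2 and 5.5.1 require withdrawal from IMP.
3. If the subject is in the mITT set (one dose and one post-dose ACR20 evaluation), SAP 16.1 makes the Week 12 outcome a non-response. No replacement is randomised.
4. If the drug is stopped before dosing, no withdrawal follows. However, exclusion 24 gives no stopping interval for this class.
5. Either way, a medical reviewer who applies the PDEV35 text to drug use at entry would record a breach of exclusion 24 that did not occur.

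**What the label can affect.** SAP 10.1 defines clinically important deviations as those leading to exclusion from an analysis set. SAP 12.2.2 gives concomitant-medication violations under 6.5.2 as possible grounds for PK/PD exclusion. No per-protocol analysis is planned, and mITT membership does not depend on deviations.

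**Figures, for background only.** Exact enumeration of the Miettinen-Nurminen score test at 30 per arm, 0.46 v 0.21 and 1-sided 10% gives 80.3% power, against the stated 80.2%. The enrolment figure also reproduces: 60 / (1 − 0.0625) = 64. If an assumed share *w* of each arm were withdrawn for this reason and counted as non-responders, irrespective of how they would have responded, the rates become 0.46(1 − *w*) and 0.21(1 − *w*):

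| Assumed *w* | Rates | Power |
|---|---|---|
| 2% | 0.451 v 0.206 | 79.3% |
| 5% | 0.437 v 0.200 | 77.6% |
| 10% | 0.414 v 0.189 | 74.7% |

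The documents give no value for *w*.

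**The case against.** The best case against is that entry and on-treatment lists need not match, and that other text closes the gap. Inclusion 11 requires subjects to comply with the protocol, which includes 6.5.2. Medications are recorded from consent, eligibility is rechecked on Day 1, and sites have up to 28 days of screening in which to notice the drug. The discretion sentence in 5.5.1 softens the withdrawal rule. Table 2 is itself imperfect: the note on moderate agents calls an inducer that lowers AUC by 50% to 80% strong.

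Part of this stands. An attentive site may well stop the drug in time, the discretion sentence does blur the rule, and the inducer boundary is unclear. But none of it extends exclusion 24 to moderate agents or says that IMP may continue. Protocol 6.5.1 also keeps drugs prohibited under 6.5.2 outside its own discretion clause.

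Four stronger readings are tempting and are not supported:
- *That the SAP codes moderate inducers as entry violations.* PDEV35 names no inducers of any strength.
- *That every such subject must be withdrawn.* This follows only if the agent continues after randomisation.
- *That the deviation check misses inducers.* PDEV35 also fires when exclusion 24 is ticked Yes, and PDEV36 and PDEV41 cover prohibited drugs on trial. The row text is incomplete, but no material loss of capture is shown.
- *That the primary result is shifted by a known amount.* The number affected is unknown, a withdrawal lowers a rate only if that subject would have responded, and baseline drug use precedes 1:1 randomisation, so there is no reason to expect it to favour one arm.

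**Conclusion.** The inconsistency is real. The entry rule is narrower than the on-trial rule for both inhibitors and inducers, and following it as written admits subjects who meet a mandatory IMP stop if they carry on with a moderate agent. PDEV35 matches neither protocol passage: it is wider than exclusion 24 for moderate inhibitors, food and CYP3A substrates, and narrower for inducers.

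The conclusion assumes that potent means strong, which is the natural reading but is not stated. No size of effect is claimed, and the power figures above are conditional arithmetic on assumed shares. The PDEV35 mismatch reaches the deviation tables and possibly PK/PD set membership, but not the primary analysis set. Which CYP3A classes should be barred, and when, is a clinical decision on which this review takes no position.

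**What to change.** Reconcile Protocol exclusion 24 with Sections 6.5.2 and 5.5.1 so that the entry and on-trial rules name the same CYP3A classes in the same defined terms, with the sponsor choosing them. In the same clarification, state whether the discretion sentence in 5.5.1 affects continuation of IMP. Then reword PDEV35 to match the reconciled exclusion 24, including inducers and the narrow-index limit, and leave on-trial use to PDEV36 and PDEV41.

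The cost is a protocol clarification and one row of SAP Appendix 3. The primary analysis method and the sample size do not change.
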